6. **Lung Cancer Screening Uptake** is the primary outcome and will be assessed via self-report via the stages of adoption algorithm for lung screening. The algorithm for collecting this item presents additional questions conditional on responses (see Appendix D). There are seven stages (*unaware, aware but unengaged, undecided, decided not to act, decided to act, action, and maintenance*). This will help to understand screening behavior more robustly by understanding the stages of decision-making and adoption (i.e., uptake) of the behavior. Please note that screening uptake is considered stages 6 and 7 (action and maintenance).

The description of lung cancer screening with LDCT of the chest developed in our preliminary studies includes a picture and a written description of an LDCT. This description is embedded in the follow up surveys (Appendix C) prior to the self-reported question to ensure participants understand the question. Using the same successful procedure as in our prior pilot RCT for LungTalk,⁴⁵ we will verify screening for individuals who self-report completing an LDCT of the chest to screen for lung cancer by mailing an authorization form to be signed and mailed back to the research office. Trained research staff will verify the screening LDCT scan using the information and signed authorization form by contacting the facility directly to request confirmation.

7. **Upcoming Primary Care Provider Visit** will be measured with one item: Do you have an appointment already scheduled to follow-up with your primary care provider? If yes, when?

In order to generate a robust semi-structured interview guide about the sustainability of a social media-based approach to increasing lung screening awareness and uptake, key stakeholder participants representing administrators (healthcare system and screening centers), key screening center personnel, advocacy organizations (i.e., LUNGevity, Dusty Joy Foundation), and national organizations (American Cancer Society, American Lung Association, GO₂ Foundation for Lung Cancer) will be conducted. We will begin the Key Stakeholder participant recruitment no earlier than Year 3 of the study. These stakeholder participants will complete one semi-structured interview that will take 45-60 minutes to complete. We will amend the protocol to include the semi-structured interview guide that will be informed and created from the quantitative data collected from the participants.

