5.7. Follow-up and end-of study (if applicable) n/a

5.8. Statistical Method

This behavioral intervention study will randomize 500 screening-eligible individuals in a 1:1 ratio into the *LungTalk* intervention or the non-tailored video intervention condition. We will use descriptive statistics such as means, standard deviations, and frequency distributions/distributional assumptions to examine data quality, identify patterns of missing and out-of-range values, and evaluate parametric assumptions. Remediation of normal distribution assumption violations will be accomplished using the Box-Cox procedure for transformations. We will apply the intention-to-treat (ITT) principle in handling missing data on screening uptake; a study participant will be coded as 'no screening uptake' unless otherwise verified by our participation sites. We will examine violations of the missing-at-random assumption for secondary outcomes. If missingness is associated with any

observed characteristics, then covariates associated with missingness will be incorporated into a sensitivity analysis to minimize bias.

Aim 1. Examine the use of a social media platform (i.e., Facebook) to reach high-risk individuals eligible for lung screening. We will describe and compare the following measures and metrics using a mixture of data from FB analytics and study data from REDCap.

Goal	Analytic Plan
Estimate the number and percentage of individuals aged 50 and older who currently or formerly smoke in the population that the advertisement is marketed.	Numerator = # of Facebook members age 50+ who currently or formerly smoke in target markets Denominator = total # of Facebook members in target markets Both numerator and denominator provided by FB Analytics.
Estimate the approximate percent of this population to which this advertisement is marketed are eligible for lung screening according to the USPSTF guidelines.	Numerator = # of eligible participants, among those screened. Denominator = total number screened. Data from screening survey.
Record the percent of eligible participants who agree to participate in the study.	Numerator = total number consented Denominator = # of eligible participants
Compare differences between those participating and those not participating on smoking status (i.e., current vs. former), age, gender, geography, and other key variables collected on the screening survey.	Descriptive tables along with a series of independent samples t-tests and Chi-square tests.

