5.8.2. Statistical Analysis Plan

With a sample size of n=250 per intervention group, and using an ITT analysis (default is no screening uptake unless otherwise verified, thus no "missing" outcome data), we will be able to detect a difference between the *LungTalk* and non-tailored educational video groups with an 80% statistical power if the difference in lung screening uptake at 6-month follow-up (primary outcome) is 25% in the *LungTalk* group compared to 15% in the non-tailored educational video groups, in a test of independent proportions and a two-sided type-I error rate of 5%. This 25% vs. 15% comparison is a conservative estimate, as 31% vs. 10% difference was observed in preliminary data testing *LungTalk* in a sample of community-based screening-eligible individuals in Indiana in 2018 using the same ITT procedure.¹⁶

6 - Trial Administration

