6.4. Informed consent

All participants (N=500) (except stakeholders) will sign an e-consent in REDCap.

The consent form/research authorization meets the requirements of the Code of Federal Regulations and the Institutional Review Board/Privacy Board of HMH. The consent form will include the following:

1. The nature, objectives, potential risks, and benefits of the intended study.
2. The length of study, what it entails, and the likely follow-up required.
3. Alternatives to the proposed study.
4. The name of the investigator(s) responsible for the protocol.
5. The right of the participant to accept or refuse study interventions/interactions and to withdraw from participation at any time.
6. How the participants' data will be protected, who will have access to their PHI, and what data will be disclosed for research purposes.

Prior to inclusion in the study and before protocol-specified procedures are carried out, potential participants will be able to read the full details of the protocol as outlined in the consent and research authorization. Participants will have the ability to contact the investigator if there are any questions prior to consenting electronically. Participants will also be informed that they are free to withdraw from the study at any time.

All participants must electronically sign an IRB-approved consent form via REDCap indicating their consent to participate. A consenting professional signature is not required as noted in IRB SOP IC-706. The participant will be offered to receive a copy of the signed informed consent form either by email or by mail.

Key stakeholder participants (N=20) will be consented over the phone using a verbal consent.

The verbal informed consent/research authorization meets the requirements of the Code of Federal Regulations and the Institutional Review Board/Privacy Board of HMH. The consent/research authorization script will include the following:

1. The nature, objectives, potential risks, and benefits of the intended study.
2. The length of study, what it entails, and the likely follow-up required.
3. Alternatives to the proposed study.
4. The name of the investigator(s) responsible for the protocol.
5. The right of the participant to accept or refuse study interventions/interactions and to withdraw from participation at any time.
6. How the participants' data will be protected, who will have access to their PHI, and what data will be disclosed for research purposes.

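### Letting participants e-sign the scan-verification release in REDCap, with the mailed form as back-up, is a cheap way to gain verified primary events and power

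*Combined protocol and SAP*

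**What the plan says.** - **Verification route (5.5 item 6).** A participant who reports a screening scan is verified "by mailing an authorization form to be signed and mailed back to the research office". Research staff then use the signed form to ask the facility for confirmation. The section says the pilot trial of LungTalk used this procedure successfully. It gives no return rate, no reminder schedule and no electronic alternative.
- **Coding rule (5.8 and 5.8.2).** Screening uptake at 6 months is the primary outcome. For the power statement the rule is "default is no screening uptake unless otherwise verified", and 5.8 gives the same rule for the analysis.
- **Existing electronic signing (6.4).** "All participants must electronically sign an IRB-approved consent form via REDCap indicating their consent to participate". Section 6.4 describes the document as a consent form together with a research authorization.
- **Existing online surveys (5.6).** Participants enter their answers directly in REDCap after automatic invitations.
- **Power (5.8.2).** "With a sample size of n=250 per intervention group", the plan claims 80% power for 25% uptake with LungTalk "compared to 15% in the non-tailored educational video groups", using a two-sided 5% test of independent proportions.

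**The concern.** Eligibility, consent, baseline and follow-up surveys and the intervention all reach the participant electronically. The release for scan verification is the one step that asks a participant to receive a letter, sign it and post it back, and a primary event depends on it. Because unverified means no, a lost or ignored form does not produce a missing value. It turns a true event into a non-event.

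If forms are lost at the same rate in both arms, observed uptake in each arm is the true uptake multiplied by the return rate, and the absolute difference shrinks by the same factor. Asking for the signature when the scan is reported, with a tool the trial already uses, could recover some of those events without recruiting anyone else.

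**Working it through.** **Inputs from the documents.** 250 per arm (5.8.2), allocated 1:1 from 500 (5.8); uptake 25% vs 15%; two-sided alpha 5%; stated power 80% (all 5.8.2). Unverified scans count as no uptake (5.8, 5.8.2).

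**Inputs that are assumptions.** The share of true scans verified by post, r_m, and the share verified once e-signature is offered first, r_e. The documents give neither. Both are taken as equal across arms.

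**Step 1: reproduce the stated power.** With p̄ = (p1 + p2)/2,

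power = Φ( [ (p1 − p2) − 1.96·√(2p̄(1−p̄)/n) ] / √( (p1(1−p1) + p2(1−p2))/n ) ).

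For p1 = 0.25, p2 = 0.15, n = 250:
- p̄ = 0.20, and the null standard error is √(2 × 0.20 × 0.80/250) = 0.03578.
- The alternative standard error is √((0.1875 + 0.1275)/250) = 0.03550.
- z = (0.10 − 1.96 × 0.03578)/0.03550 = 0.842, so power is 80.0%.

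The plan's figure reproduces.

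**Step 2: are 25% and 15% before or after verification loss?** Section 5.8.2 states them inside the sentence that sets the unverified-means-no rule. It then compares them with a pilot result of 31% vs 10% obtained under the same intention-to-treat procedure. The natural reading is that they are verified rates, already net of whatever the postal step loses.

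**Step 3: main reading, verified rates.** True rates are then 0.25/r_m and 0.15/r_m. Verified rates under better capture are 0.25·k and 0.15·k, with k = r_e/r_m. Expected verified events now are 250 × 0.25 + 250 × 0.15 = 100, and they become 100·k.

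| Capture by post → with e-signature (assumed) | k | Verified rates | Expected events | Power |
|---|---|---|---|---|
| no change | 1 | 25.0% vs 15.0% | 100 | 80.0% |
| 90% → 95% | 1.056 | 26.4% vs 15.8% | 106 | 82.6% |
| 80% → 85% | 1.0625 | 26.6% vs 15.9% | 106 | 82.9% |
| 80% → 90% | 1.125 | 28.1% vs 16.9% | 112.5 | 85.6% |
| 80% → 95% | 1.1875 | 29.7% vs 17.8% | 119 | 87.9% |

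**Step 4: alternative reading, true scan rates before any loss.** Verified rates are 0.25·r and 0.15·r.

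| Return r (assumed) | Verified rates | Power | n per arm for 80% |
|---|---|---|---|
| 95% | 23.75% vs 14.25% | 77.4% | 267 |
| 90% | 22.5% vs 13.5% | 74.7% | 285 |
| 80% | 20.0% vs 12.0% | 68.5% | 329 |
| 70% | 17.5% vs 10.5% | 61.7% | 385 |

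On this reading, moving return from 80% to 95% raises power from 68.5% to 77.4%.

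**The case against.** **The postal route was chosen for a reason.** The protocol cites successful use in the pilot, and nothing contradicts that. This stands: the procedure is not an error. But no return rate is reported, so the pilot's success does not show that loss was small.

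**A reader might infer that the trial is underpowered, at 62% to 75%.** That needs 25% and 15% to be rates before verification loss, and the wording of 5.8.2 points the other way. If the pilot's 31% vs 10% held, power would stay above 97% even at 50% return. The stronger claim is not supported.

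**A reader might infer that participants have already e-signed the necessary release.** Section 6.3 describes the research authorization as governing use and disclosure that the sponsoring institution may allow. The mailed form is used to obtain confirmation from an outside facility. The documents do not show that one covers the other. They establish only that participants can and do sign in REDCap.

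**Facilities may not accept an electronic signature.** Section 4.3.c counts 126 certified screening centers in the five recruitment states, and nothing says what such facilities require. This also stands. It could reduce the gain considerably, but with the mailed form kept as fallback those cases are handled as now.

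**The loss really comes from the coding rule.** Section 5.5 item 6 also defines uptake by self-reported stage (action or maintenance), and on that definition alone the form's route would cost no primary events. The two definitions do need reconciling. As 5.8 and 5.8.2 are written, however, verification decides the outcome.

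**Conclusion.** This is a worthwhile, low-cost improvement and not a fault in the power calculation. The mechanism follows from the plan's own text: a release obtained only by post, combined with a rule that counts unverified scans as no uptake, turns non-return into lost primary events.

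The stated 80% stands on the natural reading. The benefit is then about 3 points of power for a 5-point improvement in capture, and up to about 8 points for an improvement from 80% to 95%. Those capture rates are illustrations; 95% with e-signature is the optimistic end. Only if 25% and 15% are pre-verification scan rates would planned power fall below 80%.

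The calculation assumes equal capture in both arms, and the documents give no information on return by arm. That e-signature would raise capture at all is a reasonable inference and not something the documents establish. With the paper route retained in full, there is no evident reason it should lower it.

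**What to change.** Amend 5.5 item 6 so that reporting a low-dose CT in a REDCap survey opens, in that survey, a release for e-signature that also asks for the facility name and scan date. Keep the mailed form for participants who do not sign online and for facilities that require paper. Eligibility, randomization, the interventions and the coding rule are unchanged.

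Also state in 5.8.2 whether 25% and 15% are verified rates, and give the pilot's form-return rate if it is known. That would replace the assumed range above with an actual figure.

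The cost is one REDCap form, an IRB amendment and a verification procedure that no longer matches the pilot's exactly. Before building it, ask a few facilities whether they accept an electronically signed release, since the size of the gain depends on the answer.

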5.6. Data management (data collection, source, and storage)

Data collected for this study will be entered into and managed via a secure REDCap Database. REDCap, Research Electronic Data Capture, is an open-source platform that allows for the collection of research data in a secure manner over a web-based interface. Usage of the platform is contingent on an open-source license. The platform was developed by Vanderbilt University which HMH has a standing agreement with to allow the usage of REDCap for academic/research purposes.

For this protocol, electronic REDCap data entry forms will be completed online by the participant. They will be auto sent survey invitations when their surveys are due. Participant responses will be recorded directly in REDCap. All connections to REDCap utilize encrypted (SSL-based) connections to ensure data is protected.

User access to the data is contingent on those a part of the study team and data sharing agreements in place with third party entities, if applicable. Project managers are responsible for regularly auditing these permissions to ensure changes in staff are reflected appropriately.

REDCap has the ability maintain an audit trail of changes to the database providing a timestamp as well as the user making the update. In addition, a data resolution module offers the ability of opening and closing queries optionally requiring justification when data is being updated. Permission roles for data resolution are integrated in REDCap. Comprehensive system logs are also maintained of user activity and when changes to the database are made.

Final data sets for publication are required to be locked and stored centrally for potential future access requests from outside entities.

Audio recorded data from the key stakeholder interviews will be stored on an CDI/HMH passphrase-protected server until transcribed. Audio recorded data from stakeholder participants will not include any identifying information and will be used to produce a de-identified verbatim transcript and erased after transcribed.

5.7. Follow-up and end-of study (if applicable) n/a

5.8. Statistical Method

This behavioral intervention study will randomize 500 screening-eligible individuals in a 1:1 ratio into the *LungTalk* intervention or the non-tailored video intervention condition. We will use descriptive statistics such as means, standard deviations, and frequency distributions/distributional assumptions to examine data quality, identify patterns of missing and out-of-range values, and evaluate parametric assumptions. Remediation of normal distribution assumption violations will be accomplished using the Box-Cox procedure for transformations. We will apply the intention-to-treat (ITT) principle in handling missing data on screening uptake; a study participant will be coded as 'no screening uptake' unless otherwise verified by our participation sites. We will examine violations of the missing-at-random assumption for secondary outcomes. If missingness is associated with any

observed characteristics, then covariates associated with missingness will be incorporated into a sensitivity analysis to minimize bias.

Aim 1. Examine the use of a social media platform (i.e., Facebook) to reach high-risk individuals eligible for lung screening. We will describe and compare the following measures and metrics using a mixture of data from FB analytics and study data from REDCap.

Goal	Analytic Plan
Estimate the number and percentage of individuals aged 50 and older who currently or formerly smoke in the population that the advertisement is marketed.	Numerator = # of Facebook members age 50+ who currently or formerly smoke in target markets Denominator = total # of Facebook members in target markets Both numerator and denominator provided by FB Analytics.
Estimate the approximate percent of this population to which this advertisement is marketed are eligible for lung screening according to the USPSTF guidelines.	Numerator = # of eligible participants, among those screened. Denominator = total number screened. Data from screening survey.
Record the percent of eligible participants who agree to participate in the study.	Numerator = total number consented Denominator = # of eligible participants
Compare differences between those participating and those not participating on smoking status (i.e., current vs. former), age, gender, geography, and other key variables collected on the screening survey.	Descriptive tables along with a series of independent samples t-tests and Chi-square tests.
Record reasons that participants refuse to participate in the study.	Descriptive analysis from screening survey data.
Estimate attrition at 1 week and 6-month follow-up time periods.	Numerator = # of baseline participants - # of participants who complete the follow-up assessment (either 1 week or 6 month) Denominator = # of baseline participants Completion at follow-up defined as completing, at the least, the screening/stage of adoption item.
Compare differences between those completing and those not completing the study on sociodemographic and health status variables, geography, baseline scores on knowledge, lung cancer screening health beliefs, and stage of adoption for lung cancer screening.	Descriptive tables along with a series of independent samples t-tests and Chi-square tests. Completion of the study is defined as completing the screening uptake item for the 6-month assessment.

Aim 2. Compare the effectiveness of a computer-tailored health communication and decision support tool (LungTalk) to a non-tailored Lung Screening Informational Video on lung screening: 1)

knowledge; 2) health beliefs (perceived risk, perceived benefits, perceived barriers, self-efficacy); 3) occurrence of a patient-clinician discussion about lung screening; and 4) uptake and completion (primary outcome). Total knowledge scale scores and Lung Cancer Screening Health Beliefs (total scale scores for perceived risk, perceived benefits, perceived barriers, self-efficacy) are continuous variables. Occurrence of patient-clinician discussion and screening uptake are dichotomous variables. Prior to group comparisons, measures will be described by timepoint, both overall and by group. Within-group changes will be assessed using standardized effect sizes. The primary outcome is screening uptake at 6-month follow-up. For between-group comparisons, generalized linear models will be used with adjustment for smoking status; appropriate link functions for each outcome will be determined based on distributions (e.g., for dichotomous outcome variables we will use a logit link). In the case of differential attrition, as noted above, a sensitivity analysis will be conducted such that regression models will also include baseline covariates that differ significantly between participants who do and do not complete follow-up assessments.

Aim 3 (Qualitative). Explore the sustainability of a social media-based approach among key stakeholders to increase lung screening awareness, knowledge, adoption and uptake among screening-eligible individuals. (Note: Sustainability is defined as the extent an evidence-based intervention can deliver its intended benefits over an extended period of time within practice based upon the Dynamic Sustainability Framework.¹¹) Audio recordings will be transcribed verbatim. [name] will read and verify each transcript. Drs. [name] and [name] will analyze the transcripts with the aid of QRS International's NVivo10, a qualitative data analysis program, using conventional content analysis techniques. Each text unit (meaningful phrase, sentence, or story relevant to the study aims) will be extracted and coded with a short phrase reflecting its essence. Codes will be displayed on a case-by-variable matrix as described by Miles, Huberman, and Saldaña. Using data from the in-depth interviews, the research team will first categorize codes in each column and provide a description of each category. This will yield an in-depth description of factors that contribute to sustainability. All transcribed interviews will be validated for accuracy by [name]. Because the initial coding of the data involves a low level of interpretation, a clinical research coordinator will code the data and place each code in the relevant cell of the data display table. [name] will verify the coding. Coding will be further verified by the investigators during a data analytic team meeting. Disagreements about code labels or placement will be resolved by a reevaluation of transcript data and team discussion until consensus is reached. The categorization of the data in each column, which involves a higher degree of interpretation, will be done by team discussion to reach consensus. Because the findings will be produced in an evolving and iterative process, inter-coder reliability indices are not feasible; however, a detailed and systematic plan to ensure negotiated consensual validity at each stage of analysis will ensure credibility of the findings, and a detailed audit trail will be maintained that chronicles all analytic decisions. All digital recordings will be saved on a passphrase protected HMH server and deleted 7 days after verification of the transcript for accuracy. Only the PI and Research Project Associate will have access to the digital recordings.

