3. **Total Knowledge of Lung Cancer Screening** will be assessed with a 9-item multi-dimensional scale used in our preliminary study adapted from literature specific to lung cancer.¹⁶ Several aspects will be assessed, including knowledge of lung cancer, risk, and screening. The range of scores is 0 to 9.
4. **Lung Cancer Screening Health Belief Scales** described in the preliminary studies section will be used to measure perceived risk, perceived benefits, perceived barriers, and self-efficacy. Content and construct validity have been established. Internal consistency reliability was established by our team with a sample of 497 screening-eligible long-term smokers:
 - i. *Perceived Risk of Lung Cancer* is a 3-item scale with Likert-type responses. The range of scores is 3 to 12 (higher perceived risk of lung cancer). Cronbach's α was 0.88 in our preliminary study.¹⁶
 - ii. *Perceived Benefits of Lung Cancer Screening* is a 6-item scale with responses ranging from 1=strongly disagree to 4=strongly agree. The range of scores is 6 to 24 (higher perceived benefits) with a Cronbach's α of 0.76 in our preliminary study.¹⁶
 - iii. *Perceived Barriers to Lung Cancer Screening*. This scale has 17 items with four-point Likert responses where 1=strongly disagree and 4=strongly agree. The range of scores is 17 to 68 (higher perceived barriers) with a Cronbach's α of 0.87 in our preliminary psychometric study.¹⁶
 - iv. *Self-Efficacy for Lung Cancer Screening*. This scale has 9 items with a four-point Likert response option to assess individual beliefs about ability to arrange and complete an LDCT to screen for lung cancer. The range of scores is 9 to 36 (higher levels of self-efficacy) with a Cronbach's α of 0.92 in our preliminary psychometric study.¹⁶
5. **Occurrence of a Patient-Clinician Discussion about Lung Cancer Screening** will be assessed with a single item requiring dichotomous (Y/N) response: Have you had a discussion with your primary care clinician about lung cancer screening?

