5.8.1. Sample size calculation and justification

With a sample size of n=250 per group and up to 20% missing assessment data (n=200 available for analysis) on total knowledge scale and total perceived risk scale scores (secondary outcomes), we will have an 80% statistical power if the difference is d=0.28 (in standardized effect size units, or Cohen d), in an independent-sample t-test with a two-sided type-I error rate of 5%. A 0.25 effect is what Cohen considered a 'small' effect size in psychology research, thus a conservative estimate of the statistical evidence that can be supported in our study design.

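### Box-Cox is the stated remedy for non-normal scores, but the 0–9 knowledge score allows zeros, no shift is fixed and the link is left open, so the scale of this secondary effect is not set in advance

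*Combined protocol and SAP*

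**What the plan says.** Three parts of the plan bear on how the scale scores are analysed.

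- **Remedy for non-normality (5.8, opening paragraph).** "Remediation of normal distribution assumption violations will be accomplished using the Box-Cox procedure for transformations". The sentence is not limited to particular outcomes. It gives no test or threshold for a violation, no rule for choosing lambda and no shift constant.
- **Score ranges (5.5, items 3 and 4).** For knowledge, "The range of scores is 0 to 9". The four belief scales start above zero: perceived risk ("The range of scores is 3 to 12"), benefits ("The range of scores is 6 to 24"), barriers ("The range of scores is 17 to 68") and self-efficacy ("The range of scores is 9 to 36").
- **Between-group model (5.8, Aim 2).** Generalized linear models adjusted for smoking status, where "appropriate link functions for each outcome will be determined based on distributions". The only example is a logit link for binary outcomes. The same paragraph classes the knowledge and belief totals as continuous.

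Section 5.8.1 calls knowledge and perceived risk secondary outcomes. It powers them with an independent-sample t-test at a difference of 0.28 "in standardized effect size units, or Cohen d", with 200 per arm and a two-sided 5% level. The primary outcome in 5.8 is screening uptake at 6 months, which is binary.

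**The concern.** Standard one-parameter Box-Cox needs strictly positive data, and the plan names it as the remedy for a set of outcomes that includes one with a floor of 0. If the remedy is triggered and anyone scores 0, the analyst must improvise: add a constant, choose its size, or do something else. The plan settles none of this.

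The link sentence adds a second choice that depends on the observed distribution of the same outcome. Nothing says which device is tried first, whether both may be used, or on which scale the knowledge effect will be reported.

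What is at stake is prespecification and interpretability. A difference on a scale defined by an estimated lambda and an arbitrary constant is neither a difference in knowledge points nor the standardized difference used in the power statement.

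**Working it through.** **1. The plan's power figure.** Inputs from 5.8.1: d = 0.28, n = 200 per arm, two-sided 5%.

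Power ≈ Φ(d·√(n/2) − 1.96) = Φ(0.28 × 10 − 1.96) = Φ(0.84) = 80.0%. The exact noncentral-t value is 79.8%. The stated 80% reproduces, on the raw-score t-test scale.

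**2. Box-Cox at zero.** The transform is (y^λ − 1)/λ, or log y when λ = 0. The log-likelihood for λ contains (λ − 1)·Σ log y.

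- λ < 0: y = 0 means division by zero.
- λ = 0: log 0 is minus infinity.
- λ > 0 and fixed: y = 0 maps to −1/λ, which is finite.
- λ estimated: Σ log y is minus infinity, so the estimate is not available. A standard routine run on data containing a 0 stops because the data must be positive.

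So what breaks is the estimation of lambda. The belief scales, with minimums 3, 6, 17 and 9, are not affected.

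**3. How likely is a zero?** The documents give no knowledge mean or SD, so this rests on assumptions. With nine independent items and proportion correct p, P(score 0) = (1 − p)^9 and P(at least one zero in 400) = 1 − [1 − (1 − p)^9]^400. For p = 0.5: 0.5^9 = 0.00195, giving 54%. The last column uses a beta-binomial score with item correlation 0.1.

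| Assumed proportion correct | Independent items | Item correlation 0.1 |
|---|---|---|
| 0.3 | 100% | 100% |
| 0.4 | 98% | 100% |
| 0.5 | 54% | 99.9% |
| 0.6 | 10% | 88% |
| 0.7 | 0.8% | 43% |

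A zero is close to certain if knowledge is low, and may not occur if it is high.

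**4. What a shift does.** Simulation: beta-binomial 0–9 scores, item correlation 0.15, true shift d = 0.28 in control-SD units, 200 per arm, 1,500 runs, constants 0.1, 0.5 and 1.

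| Control proportion correct | Power, raw t-test | Power, shifted Box-Cox | Mean λ |
|---|---|---|---|
| 0.3 | 77.9% | 79.1–79.3% | 0.45–0.56 |
| 0.5 | 78.3% | 78.2–78.6% | 0.90–0.96 |
| 0.7 | 83.3% | 83.9–84.5% | 1.68–1.91 |

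Type I error was 4.1–5.1% throughout. Monte Carlo error for power is about 1 point. The transformation changes power by at most about 1.5 points, but lambda runs from about 0.45 to 1.91 with the assumed distribution and also shifts with the constant. The reporting scale therefore depends on the data.

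**5. What baseline adjustment adds.** Adjusting for a baseline score with correlation ρ to follow-up shrinks the residual SD by √(1 − ρ²), so the effective d is 0.28/√(1 − ρ²). The documents give no ρ, so a range is shown (normal approximation; the t-based value in step 1 ran about 0.2 points lower).

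| Assumed ρ | Effective d | 10·d − 1.96 | Power |
|---|---|---|---|
| 0 | 0.280 | 0.84 | 80% |
| 0.3 | 0.294 | 0.98 | about 83% |
| 0.4 | 0.306 | 1.10 | about 86% |
| 0.5 | 0.323 | 1.27 | about 90% |
| 0.6 | 0.350 | 1.54 | about 94% |

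**The case against.** The best defence is that the sentence is conditional and the statisticians will handle zeros sensibly. Box-Cox is invoked only if normality is judged violated, and the name can be read to include the shifted two-parameter form, which runs. The link sentence can be read as matching the model to the outcome type, with identity the ordinary choice for a score classed as continuous. A link acts on the mean and Box-Cox on the data, so the two do not contradict each other. All of this stands, and it is why the point is minor. What it does not supply is a shift, a trigger or an order of precedence.

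Three stronger readings are tempting, and the documents support none of them.

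- **That the knowledge analysis must break down.** It does so only if a violation is declared, a zero is observed and no shift is used.
- **That zero scorers would be excluded, with a loss of power.** No section says to exclude anyone. The loss from doing so would also hinge on an assumed mean. In a beta-binomial simulation (d = 0.28, 200 per arm, item correlation 0.10–0.20), power after exclusion was 58–67% at a control mean of 3, but 76–78% at a mean of 5 (raw scores 80–81%) and 80–81% at a mean of 6 (raw 82%).
- **That type I error is materially inflated.** This needs the analyst to report the smallest p-value over several transformations, a practice the plan does not describe. Each single method kept close to 5%.

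It can also be said that baseline adjustment goes beyond the zero problem. It does, but it belongs in the same sentence of the plan and uses data already collected.

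**Conclusion.** The point holds as a minor prespecification gap. The named remedy cannot be fitted in its standard form to a 0–9 score containing a zero, no shift is fixed, and the link is separately left to the observed distribution. The scale of the knowledge effect is thus open until the data are seen and may differ from the scale on which the outcome was powered.

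The practical cost is mainly interpretability. Across the assumed score distributions, the choice between raw and shifted Box-Cox scores made almost no difference to power or type I error at 200 per arm, so the transformation also buys nothing. The zero problem is confined to knowledge; the open choice of scale extends to the four belief scores. Screening uptake, the binary primary outcome in 5.8, is unaffected. The zero frequencies, simulated power and baseline correlations are assumptions, because the documents give no knowledge mean, SD or correlation.

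**What to change.** In 5.8, replace the Box-Cox sentence, and the open link choice for the five scale scores, with text along these lines:

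*Knowledge, perceived risk, perceived benefits, perceived barriers and self-efficacy totals will each be compared between arms on their original scale in a linear model (identity link), adjusted for smoking status and the baseline value of the same score, with robust standard errors. The effect will be reported in scale points and as a standardized difference. A rank-based test may be given as a sensitivity analysis. Binary outcomes will use a logit link.*

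The cost is one or two sentences. All five scores are already collected at T1 according to Table 1 in 5.5, while the main model in 5.8 names only smoking status as an adjustment. No new data or change in sample size is needed, and the 80% in 5.8.1 can stand as the figure without baseline adjustment.
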